9.2.8. Magnetic Resonance Imaging

All subjects will receive an MRI in this study at the time points indicated in the Time and Events scheduled for primarily safety reasons.

An additional baseline MRI may be collected (during screening or Day 1) in case subjects are enrolled from future JNJ-54861911 studies who did not obtain an adequate MRI under the parent protocol 6 months prior to first dosing in this study. For subjects who participated in study 54861911ALZ2002 no baseline MRI scan is to be collected as an MRI was collected at Month 6 under the parent protocol.

Collection of MRI data is primarily for safety reasons. MRI scans will be collected during DB treatment phase (up to and including Week 52 [Month 12]) and OL treatment phase (annual). Additional MRI scans may be collected based on emerging safety data (e.g., ARIA-E or H) with a frequency as recommended by the DRC.

Imaging sequences for all pre-specified protocol MRI studies will consist of an identical set of pulse sequences, including FLAIR and T2* sequences, as described in the MRI imaging manual.

Global and regional brain volumes and regional cortical thickness will be derived from the volumetric MRI sequence and will include both cross sectional absolute measurements and longitudinal volume change. The regional volumes and regional cortical thicknesses that will be chosen for this study will include those anatomical areas that are most affected in AD.

All MRI data collected (screening and on treatment) will be sent to a core imaging lab for quality control purposes and for data management, image processing, data analysis, and archiving.

MRI image evaluation will be performed by a core imaging lab.

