Abbreviations = CDR: Clinical Dementia Rating Scale; CFI: Cognitive Function Index; CSF: cerebrospinal fluid; C-SSRS: Columbia Suicide Severity Rating Scale; CVLT-II: California Verbal Learning Test – Second Edition; DRC: Data Review Committee; ECG: electrocardiogram ; MRI: Magnetic Resonance Imaging; MMSE: Mini Mental State Examination; OCT: Optical Coherence Tomography; PK: pharmacokinetic(s); PD: pharmacodynamics; RBANS: Repeatable Battery for the Assessment of Neuropsychological Status.

TIME AND EVENTS SCHEDULE (FOOTNOTES)

Footnotes

- ^a Subjects will self-administer study drug (once daily) with a glass of water following breakfast or a light snack. Study drug administration will take place during the morning hours. During scheduled visits when ECG or blood samples for JNJ-54861911 concentrations in plasma are to be obtained subjects will self-administer their study medication on site as described above. On Day 1 study drug administration will not be time limited.
- ^b Baseline (predose) only if no (adequate) assessment was obtained under the parent protocol at the last study visit of the treatment phase.
- ^c Must be performed predose.
- ^d At all time points, triplicate ECGs are required, i.e., 3 individual ECG tracings should be obtained as closely as possible in succession, but no more than 2 minutes apart. The full set of triplicates should be completed in less than 4 minutes.
- ^e Only if no adequate assessment was obtained under the parent protocol within 9 months of first dosing in this study.
- ^f May be performed during screening in case of logistical issues.
- ^g C-SSRS baseline: Only to be completed if no C-SSRS assessment was performed under the parent protocol; C-SSRS since last visit: to be completed if the C-SSRS assessment was performed under the parent protocol.
- ^h The RBANS will be completed first followed by the CDR and MMSE if the raters for RBANS and CDR are independent. If the raters for RBANS and CDR are the same, the CDR will be performed first, followed by the RBANS and MMSE.
- ⁱ Only if no adequate assessment was obtained under the parent protocol 6 months prior to first dosing in this study.

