4.1. Inclusion Criteria

Each potential subject must satisfy all of the following criteria to be enrolled in the study.

1. Criterion modified per amendment.
 - 1.1 Subjects in the early AD spectrum at time of enrollment meeting all pertinent inclusion and exclusion criteria of the parent protocol, must have very recently completed their treatment in a Phase 1b or Phase 2 JNJ-54861911 clinical study (e.g., 54861911ALZ2002) under the parent protocol. Enrollment in this study should be completed (Day 1 of DB treatment phase) as soon as possible, but within 6 weeks, following completion of their treatment period under the parent protocol. If not defined under the parent protocol, completion of the treatment period is defined as having completed all study related procedures of the last visit of the treatment period under the parent protocol. A screening phase of up to 12 weeks may be allowed following written approval of the Sponsor.
2. Subject must be willing and able to adhere to the prohibitions and restrictions specified in this protocol.
3. Criterion modified per amendment.

- 3.1 Each subject must sign an informed consent form (ICF) indicating that he or she understands the purpose of and procedures required for the study and are willing to participate in the study.
4. Subjects must have a reliable informant (relative, partner, or friend). The informant must be willing to participate as a source of information and has at least weekly contact with the subject (contact can be in-person, via telephone or other audio/visual communication). The informant must have sufficient contact such that the investigator feels he/she can provide meaningful information about the subject's daily function. If possible, an alternate informant meeting these criteria who can replace the primary informant should be identified prior to randomization.

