9.1.3. Double-Blind Treatment Phase

Day 1

Subjects who successfully complete the screening examination will visit the clinical site on Day 1 of the DB treatment phase during the morning hours.

Prior to dosing following (baseline) assessments will be performed:

- C-SSRS (since last visit [or baseline if no C-SSRS was collected under the parent protocol])
- Blood sample collection for plasma JNJ-54861911 concentrations
- Blood sample collection for pharmacodynamics/biomarkers
- (Optional) CSF sample collection (~12 mL) by single lumbar puncture for PK/PD/biomarker assessment (baseline) after eligibility has been confirmed, provided no on-treatment sample was collected under the parent protocol
- 12-lead ECG recording
- Adverse event and concomitant medication will be reviewed

Following assessments will be performed prior to first dose in the current study at time points mentioned below only if no adequate assessments were conducted in ALZ2002 study (the assessments listed below 6 months and 9 months prior to dosing may also be performed during the screening period in case of any logistical issues):

1. At the last study visit of the treatment period:
 - Physical examination
 - Neurological examination
 - Body weight
 - Body temperature
 - Supine and standing vital signs (systolic and diastolic blood pressure and pulse)
 - Clinical safety laboratory assessments under fasted conditions, when feasible (including hematology, serum chemistry, and urinalysis)
2. 6 months prior to first dosing in this study (the assessments listed below may also be performed during the screening period in case of any logistical issues):
 - MRI
3. 9 months prior to first dosing in this study (the assessments listed below may also be performed during the screening period in case of any logistical issues):
 - Dermatological Examination

- Ophthalmological Examination (only in subjects completing the ALZ2002 parent study)
- Optical Coherence Tomography (OCT; at sites where OCT is available, in subjects completing the 54861911ALZ2002 parent study)

Eligible subjects will be assigned on Day 1 predose to the same treatment regimen in this study as received under 54861911ALZ2002 study as described in Section 6, Dosage and Administration.

Study medication will be dispensed (incl. drug accountability) and administered as outlined in Section 6, Dosage and Administration. Subjects will self-administer their study medication q.d. as instructed.

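### Section 9.2.8 rules out a baseline MRI for ALZ2002 subjects, while Section 9.1.3 and schedule footnote i call for one when no adequate parent scan exists

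*Protocol*

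**What the plan says.** Three places in the protocol govern the baseline MRI.

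- **Section 9.2.8 (Magnetic Resonance Imaging).** "For subjects who participated in study 54861911ALZ2002 no baseline MRI scan is to be collected", the reason being "as an MRI was collected at Month 6 under the parent protocol". The only fallback reads "An additional baseline MRI may be collected (during screening or Day 1) in case subjects are enrolled from future JNJ-54861911 studies", for those without an adequate parent scan in the 6 months before first dosing. The verb is permissive, and ALZ2002 subjects are outside it.
- **Section 9.1.3 (Double-Blind Treatment Phase, Day 1).** A list of assessments is to be performed before the first dose "only if no adequate assessments were conducted in ALZ2002 study". MRI is the sole entry under the 6-month look-back. ALZ2002 is named.
- **Time and Events Schedule.** MRI is marked on Day 1 under footnote i: "Only if no adequate assessment was obtained under the parent protocol 6 months prior to first dosing in this study". No parent study is exempted. The next MRI in the schedule is at Week 24, then Week 52.

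Two uses of MRI depend on a starting point. Section 3.2 describes safety MRIs as monitoring for treatment-emergent abnormalities, including ARIA-E and ARIA-H. Section 11.4.1.2 summarizes change from baseline in brain volume and cortical thickness.

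**The concern.** Section 9.2.8 is where a site would look for MRI instructions. It takes for granted that every ALZ2002 subject arrives with a usable Month 6 scan. The same section sends all scans to a core imaging lab for quality control, so the protocol itself recognizes that a scan can fail. Section 9.2.7 deals with the parallel situation for OCT and ophthalmology by an adequacy condition that does apply to ALZ2002 subjects. Section 9.2.8 is therefore out of step with its neighbour as well as with the schedule.

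At stake is the baseline for a safety assessment in a study whose primary objective is safety. Section 3.2 justifies the placebo group partly because microhemorrhages and ARIA-E are hard to separate from aging or disease. A subject first scanned here at Week 24 offers no way to tell whether a lesion was present at entry to this study. The volumetric summary is exposed in the same way.

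**Working it through.** The protocol states no sample size, power or event count that bears on this point, so the check is a comparison of the rules by type of subject, plus one timing calculation.

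**Step 1. Can an adequate Month 6 scan be too old?** Section 4.1 requires Day 1 to fall as soon as possible, "but within 6 weeks, following completion of their treatment period under the parent protocol"; a screening phase of up to 12 weeks is possible with written sponsor approval. The look-back is 6 months, about 26 weeks.

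- Usual limit: 6 weeks < 26 weeks.
- Extended limit: 12 weeks < 26 weeks.
- If the Month 6 scan was taken 28 days early (the MRI window of this study, assumed here for the parent study): 12 + 4 = 16 weeks < 26 weeks.

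An adequate Month 6 scan always passes the age test.

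**Step 2. The rules side by side.**

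| Subject | Section 9.2.8 | Section 9.1.3 / footnote i | Agree? |
|---|---|---|---|
| ALZ2002, adequate Month 6 scan | no scan | no scan | yes |
| ALZ2002, Month 6 scan missed or inadequate | no scan | predose scan | **no** |
| Future study, adequate scan within 6 months | no scan | no scan | yes |
| Future study, no adequate scan within 6 months | scan optional | scan called for (footnote i) | **no** (optional or required) |

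The conflict is confined to the second and fourth rows, which are the cases a fallback exists to cover.

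**Step 3. What follows if 9.2.8 is applied in row two.** The first MRI in this study is then at Week 24 (Week 20 to 28 with the 28-day window of footnote x).

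- *ARIA.* A lesion seen then may have arisen before or after Day 1. Section 11.5 tabulates presence of ARIA by treatment group, and that table can still be produced. What is lost is onset relative to entry.
- *Volumetrics.* Section 11.4.1.2 needs a baseline. No scan meeting footnote i's 6-month test would exist, unless some other adequate parent scan fell inside that window.

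**Step 4. Illustration of the unscanned interval.** The parent MRI schedule is not in the protocol. Assuming that the last readable parent scan was at parent baseline, with about 26 weeks of parent treatment, a gap of 0 to 12 weeks, and 24 weeks here: 26 + 0 + 24 = 50 weeks, to 26 + 12 + 24 = 62 weeks. This is a conditional range, not a figure the protocol supports directly.

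**The case against.** The strongest reply is that few or no subjects are touched. Section 1.1 lists ALZ2002 among the completed studies as of 6 September 2017, and entry must follow within 6 weeks, or 12 with approval. Most baseline MRI decisions for ALZ2002 subjects were therefore already past when this version was issued. The completion date is not given, so late entrants cannot be excluded. This stands as a limit on size. It does not remove the conflict, and the future-study row remains live.

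A second reply is that sites would obtain the scan anyway. Section 9.2.8 opens by deferring to the schedule, Section 9.1.3 is the Day 1 instruction, and the exempting sentence can be read as describing the expected case. This is a fair reading, and it makes the loss conditional on a site giving 9.2.8 precedence. The text does not say which section prevails.

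A third is that Section 4.1 may prevent missed scans by requiring all last-visit procedures to be completed. That applies only where the parent protocol leaves completion undefined, and it does not cover an unreadable scan.

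A reader might infer that every affected subject has no ARIA or volumetric baseline at all. The protocol does not support that. An earlier parent scan may exist and could show whether a finding is new since then. Section 11.4.1.2 does not name the baseline scan, a detail commonly left to the SAP. For subjects on active drug in the parent study, a Day 1 scan would not be a pre-drug baseline either.

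**Conclusion.** The protocol contradicts itself on the baseline MRI, in current text. The contradiction is limited to ALZ2002 subjects whose Month 6 scan was missed or inadequate, and to whether the scan is optional for future-study subjects. An outdated Month 6 scan is not a route to the problem. If 9.2.8 is followed, ARIA onset relative to entry cannot be established for such a subject, and the volumetric change may lack a baseline meeting the 6-month test.

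The number of subjects is not given and is probably small. It would be wrong to conclude that the ARIA table fails, that the placebo comparison is lost, or that all volumetric change values through Week 52 are necessarily missing: presence can still be counted, and the choice of analysis baseline is not fixed in this document. The 50 to 62 weeks depends wholly on an assumed parent scan schedule. The point merits correction because the inconsistency concerns a safety assessment and is cheap to remove.

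**What to change.** Reconcile Section 9.2.8 with Section 9.1.3 and footnote i so that a single baseline-MRI adequacy rule covers all parent studies, ALZ2002 and future ones alike, and says plainly whether the scan is required or optional when that rule is not met. Which imaging rule applies is for the sponsor to decide.

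In addition, identify any subject already enrolled without an adequate baseline scan. State how such subjects enter the ARIA and volumetric summaries, for example by flagging ARIA findings of undetermined onset and by reporting how many subjects lack a qualifying volumetric baseline.

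The cost is a wording change and a check of existing records. The schedule already provides for the Day 1 scan under footnote i, so aligning the text need not add a procedure to it.

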9.2.9. Clinical Laboratory Tests

Blood samples (under fasted conditions whenever feasible) for serum chemistry and hematology and a random urine sample for urinalysis will be collected. The investigator must review the laboratory report, document this review, and record any clinically relevant changes occurring

during the study in the adverse event section of the CRF. The laboratory reports must be filed with the source documents. The following tests will be performed at a central laboratory appointed by the Sponsor:

- Hematology Panel
 - hemoglobin -platelet count
 - hematocrit
 - red blood cell (RBC) count
 - white blood cell (WBC) count with differential

- Serum Chemistry Panel

 -sodium -potassium -chloride -bicarbonate -blood urea nitrogen (BUN) -creatinine -glucose -aspartate aminotransferase (AST) -alanine aminotransferase (ALT) -gamma-glutamyltransferase (GGT) -total and direct bilirubin -magnesium 	
 -alkaline phosphatase -creatine phosphokinase (CPK) -lactic acid dehydrogenase (LDH) -uric acid -calcium - phosphate -albumin -total protein -cholesterol -triglycerides -high density lipid protein -low density lipid protein
--	--

- Urinalysis

 Dipstick -specific gravity -pH -glucose -protein -blood -ketones -bilirubin -urobilinogen -nitrite -leukocyte esterase 	
 Flow Cytometry -RBC -WBC -epithelial cells Sediment -crystals -casts -bacteria
--	---

If there is discordance between the dipstick results and the flow cytometric results, the sediment will be examined microscopically.

The use of local laboratories is allowed in cases where initiation of treatment or safety follow-up is time-critical and the central laboratory results are not expected to be available before the need to begin dosing or if actions need to be taken for safety reasons.

9.3. Biomarkers

Biomarker analyses are dependent upon the availability of appropriate biomarker assays and clinical response rates. Biomarker analysis may be deferred or not performed, if during or at the end of the study, it becomes clear that the analysis described will not have sufficient scientific value for biomarker evaluation, or if there are not enough samples or responders to allow for adequate biomarker evaluation. In the event the study is terminated early, completion of biomarker assessments is based on justification and intended utility of the data

9.3.1. Fluid Biomarkers

9.3.1.1. CSF Biomarkers

During the DB treatment phase, all eligible subjects enrolled may have two optional CSF samples (12 mL per sample) collected by single lumbar punctures, one at baseline (only if no on-treatment CSF sample was collected under the parent protocol e.g., Month 6 CSF collection in study 54861911ALZ2002; otherwise the on-treatment CSF sample collected in 54861911ALZ2002 study may serve as baseline sample in this study) and one on-treatment (Week 52).

In the OL treatment phase (>52 weeks) it is intended to collect if possible on-treatment CSF samples every 96 weeks until study completion. Subjects may opt not to have these punctures being performed.

CSF samples should be taken at approximately the same time of day (with an allowable window of 3 hours), with the on-treatment samples being collected postdose.

During the course of the study the continuous (therapeutic) effects of JNJ-54861911 on the pathophysiological processes of AD may be reviewed by the DRC (CSF A β and CSF tau peptides or an alternate biomarker of neurodegeneration).

CSF p-tau (and possibly additional downstream markers of neurodegeneration) will be the primary CSF biomarker results used to assess and predict a potential therapeutic effect of JNJ-54861911.

CSF A β_{1-40} , is the primary CSF biomarker result used to confirm target engagement by JNJ-54861911. A β fragments of different length are produced by cleavage of the APP by BACE and the γ -secretase complex in the brain and excreted into CSF. While cleavage by BACE and γ -secretase leads to A β fragments, cleavage by α -secretase prevents A β fragment formation. BACE cleavage initiates the A β production at the N-terminal end of the A β fragment, which then is further processed at the C-terminal end by the γ -secretase complex. As A β turnover rates are rapid, inhibition of BACE results in a reduction of all A β fragments in CSF.

In addition to CSF p-tau and CSF A β ₁₋₄₀, other amyloid, AD and compound-related biomarkers in CSF and plasma may be assessed such as, but not limited to, additional A β fragments (A β ₁₋₃₇, A β ₁₋₃₈, and A β ₁₋₄₂), soluble amyloid precursor proteins (sAPP), t-tau, and additional downstream biomarkers of neuroinflammation, neurodegeneration, and neuronal injury such as VILIP-1, YKL-40 and others. Where appropriate consent is obtained, samples will also be stored for future research after the clinical study is completed (where local regulations permit).

9.3.1.2. Plasma Biomarkers

A β fragments can be measured in plasma, similar to in CSF, but are more difficult to measure due to interference with other plasma proteins. Current assays have not been validated to the same extent for plasma as for CSF.

Venous blood samples will be collected for the analysis of A β _{1-37,1-38,1-40,1-42} at the time points indicated in the Time and Events Schedule.

9.3.2. Imaging Biomarkers

9.3.2.1. Magnetic Resonance Imaging

All subjects will receive an MRI in the extension study at the time points indicated in the Time and Events Schedule for primarily safety reasons. However, potential treatment effects may be assessed with MRI as well.

See Section 9.2.8, MRI for a description on the MRI assessment.

9.4. Cognition, Function and Clinical Status

Cognitive evaluations (RBANS, MMSE, and CVLT-II) and functional measures (Cognitive Function Index [CFI]) will be applied in this study at different time points as indicated in the Time and Events Schedule to explore the subject's cognitive performance/progression and function over time.

In addition during course of the study the subject's clinical status will be assessed regularly by means of the CDR as indicated in the Time and Events Schedule.

During the course of the study on occasions when multiple cognitive assessments and clinical scales are to be performed the same visit day, the RBANS will be completed first followed by the CDR and MMSE if the raters for RBANS and CDR are independent. If the raters for RBANS and CDR are the same, the CDR will be performed first, followed by the RBANS and MMSE. For a given subject, the same sequence will be followed throughout the study.

Details on the different cognitive tests, versions and forms to be used as well as their sequence of performance will be described in a separate manual.

The RBANS and CVLT-II must be conducted by an experienced, trained, and qualified neuropsychologist.

The CDR and MMSE may be conducted by a study physician, clinical psychologist, research assistant or clinical study nurse specialist who has been trained and qualified in the study processes.

9.4.1. Cognitive Evaluations

9.4.1.1. Repeatable Battery for the Assessment of Neuropsychological Status

The RBANS is a 20 to 25 minute battery developed for cognitive assessment, detection, and characterization of dementia in the elderly as well as neuropsychological screening for younger patients⁵⁰. The time to administer is dependent on disease severity, but shorter if the participant is more impaired. The RBANS includes 12 subtests that measure the following 5 indices:(1) Attention Index consists of Digit Span and Coding; (2) the Language Index consists of Picture Naming and Semantic Fluency subtests; (3) the Visuospatial/Construction Index is made up of Figure Copy and Line Orientation subtests; (4) the Immediate Memory Index is comprised of List Learning and Story Memory subtests, and (5) the Delayed Memory Index consists of List Recall, List Recognition, Story Recall and Figure Recall subtests. Research has demonstrated that the RBANS is predictive of functional capacity (i.e., driving) in MCI patients², correlated with the CDR in MCI and AD³¹ and AD biomarkers^{22,62} and cognition¹⁷. The RBANS is administered face-to-face and available in over 30 languages and has been used in multinational clinical trials including AD trials.^{39,42,51}

